2. LIST OF ABBREVIATIONS

Abbreviation	Definition
AE	Adverse Event
BSA	Body Surface Area
DLQI	Dermatology Life Quality Index
IEC	Independent Ethics Committee
IRB	Institutional Review Board
PASI	Psoriasis Area and Severity Index
SPSS	Statistical Package for the Social Science (Software)

PFIZER CONFIDENTIAL

4. AMENDMENTS AND UPDATES

Amendment number	Date	Protocol section(s) changed	Summary of amendment(s)	Reason
1	23 July 2021	Throughout document	Spelling errors	Administrative
		Section 5 Milestones	Aligned dates with Study Report	Administrative
2	28 July 2021	Throughout document	Spelling errors	Administrative
		Section 5 Milestones	Align dates with Study Report	Administrative

PFIZER CONFIDENTIAL

[REDACTED]

5. MILESTONES

Milestone	Planned date
Start of data collection	01 September 2020
End of data collection	01 October 2020
Final study report	01 September 2021

6. RATIONALE AND BACKGROUND

Iraq has over 5 years of experience in using Enbrel as a treatment for psoriasis patients, starting in 2014 when the first psoriasis patients received the first dose of Enbrel. Dermatologists in Baghdad Teaching Hospital observed a positive response in patients with psoriasis using a biological treatment such as Enbrel, this observation discussed this during our medical to medical interaction. Local data indicates the value of adherence and efficacy to treatment with Enbrel in patients with moderate-to-severe plaque psoriasis after five years of use. This study aims to address the need for evaluating local and regional data of Enbrel use in Iraqi psoriasis patients, as there is no local published and limited regional data, currently. With the expected number of patients for this study, this would be the largest regional study for the evaluation of data on Enbrel use in Iraqi patients with moderate-to-severe psoriasis.

This study will evaluate local data available in Iraqi patients with moderate-to-severe psoriasis on Enbrel treatment with regards to efficacy, treatment-regimen adherence, and patient characterization (ie, age, gender, and smoking status).

7. RESEARCH QUESTION AND OBJECTIVES

This study aims to evaluate the efficacy of Enbrel as a biological treatment in moderate-to-severe plaque psoriasis patients in Iraq.

Primary objective: Efficacy of Enbrel in patients with moderate-to-severe plaque psoriasis by measuring baseline BSA, PASI, and DLQI scores compared to BSA, PASI, and DLQI scores after 6 months of initiation of treatment and compared to the last visit follow-up BSA, PASI, and DLQI scores.

Secondary objective:

Determine the first year adherence of patients with moderate-to-severe plaque psoriasis on a Enbrel treatment.

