8. RESEARCH METHODS

8.1. Study Design

This is a retrospective analysis of approximately 400 Iraqi patients diagnosed with moderate-to-severe plaque psoriasis that received Enbrel as treatment for disease.

Baseline, 6 months after initiation of Enbrel treatment and last visit follow-up, BSA, PASI, and DLQI scores for identified patients will be collected and used to evaluate efficacy. Patients will be further divided into 2 groups according to their adherence to Enbrel treatment (The adherent group will include the patients who were adherent to Enbrel treatment for one and seven years, and the non-adherent group will include patients who did not adhere to Enbrel). There will then be a comparison between both groups; in BSA, PASI, and DLQI scores at baseline, 6-months after Enbrel treatment, and at last visit follow-up after Enbrel treatment.

Patient demographic information (eg, age gender, disease duration) will be analyzed throughout the study.

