8.2. Setting

Patients ≥ 18 years of age will be identified from the local registry at the Dermatology Center in Baghdad Teaching Hospital. Patients diagnosed with moderate-to-severe plaque psoriasis and have been receiving Enbrel treatment for at least 1-year duration are eligible for inclusion in the study.

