8.4. Study Size

This study will include approximately 400 patients from the local registry that meet the inclusion criteria detailed in that described previously.

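### The primary objective infers efficacy from an uncontrolled before-after change in patients kept on Enbrel for at least a year; the design supports only a description of that change

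*Combined protocol and SAP*

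**What the plan says.** Section 7 (Research Question and Objectives) gives the aim as "This study aims to evaluate the efficacy of Enbrel as a biological treatment". The primary objective sets baseline BSA, PASI and DLQI against the scores "after 6 months of initiation of treatment and compared to the last visit follow-up BSA, PASI, and DLQI scores". That makes three scores at two follow-up times, or six within-patient comparisons. Sections 6 and 8.1 also use the word efficacy for what these scores will show.

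Section 8.1 (Study Design) describes the cohort: "This is a retrospective analysis of approximately 400 Iraqi patients diagnosed with moderate-to-severe plaque psoriasis that received Enbrel as treatment for disease". The only between-group contrast is by adherence: "Patients will be further divided into 2 groups according to their adherence to Enbrel treatment". Section 8.2 (Setting) makes eligible those who "have been receiving Enbrel treatment for at least 1-year duration", and Section 8.2.2 excludes shorter use. Section 8.4 (Study Size) gives about 400 patients with no calculation behind the number.

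Section 8.6 (Data Analysis) names unadjusted between-group tests only. It gives no paired analysis, significance level or decision rule for the primary comparison. Section 8.8 lists missing data as the sole limitation.

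**The concern.** An efficacy statement says what the drug did compared with what would have happened without it. Nothing in this design supplies the second half. The change from baseline can contain four components that the plan does not separate:

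- the effect of Enbrel;
- selection of patients who stayed on treatment, because anyone who stopped in the first year, including for lack of response, is removed before the 6-month score is analysed;
- regression to the mean, if patients entered treatment when their scores were temporarily high;
- other treatment. The criteria rule out other biologics but say nothing about non-biologic therapy, and Section 8.1 does not list it for collection.

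The adherence comparison does not fill the gap. Both groups were treated with Enbrel, membership depends on behaviour after baseline, and the comparison is unadjusted.

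Section 6 says there is no local published data and expects this to be the largest regional study of its kind. An efficacy headline would probably be relied on, although what the study can answer is narrower: how scores changed in patients who remained on Enbrel.

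**Working it through.** **Retention selection.** This follows from the text without arithmetic. The 6-month score is measured at month 6, but entry to the analysis depends on still being treated at month 12. The 6-month comparison is therefore conditioned on a later event. If patients who do poorly are more likely to stop, the retained mean change is biased towards improvement. The documents do not give the number who stopped in year one, so the size cannot be computed.

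**Regression to the mean: inputs.** n = 400 is from Section 8.4. That figure cannot be reproduced, because no effect size, SD, significance level or power is given. Everything else is assumed:

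- two-sided 0.05 level and a paired comparison;
- bivariate normal scores with correlation rho between baseline and follow-up;
- zero drug effect;
- patients taken as the top fraction q of a source population, selected on the baseline score itself.

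**Smallest significant change.** t(0.975, 399)/√400 = 1.966/20 = 0.098 SD of the change. Power of 80% is reached at (1.960 + 0.842)/20 = 0.140 SD of the change.

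**Expected fall with no drug effect.** Let c be the cut-off leaving fraction q above it, φ the standard normal density and λ = φ(c)/q. Then, in SD units of the source-population score:

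- fall d = (1 − rho)·λ
- variance of change s² = (1 − rho)²·(1 + cλ − λ²) + (1 − rho²)
- chance of p<0.05 = Φ(20d/s − 1.96) + Φ(−20d/s − 1.96)

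Example, q = 0.5 and rho = 0.8: λ = 0.399/0.5 = 0.798; d = 0.2 × 0.798 = 0.160; s² = 0.04 × 0.363 + 0.36 = 0.375, so s = 0.612; 20d/s = 5.2; chance 99.9%.

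Example, q = 0.8 and rho = 0.9: c = −0.842; λ = 0.280/0.8 = 0.350; d = 0.1 × 0.350 = 0.035; s² = 0.01 × 0.583 + 0.19 = 0.196, so s = 0.442; 20d/s = 1.58; chance 35%.

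Chance of p<0.05 with zero drug effect (expected fall in SD in brackets):

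| Selected | rho 0.6 | rho 0.7 | rho 0.8 | rho 0.9 |
|---|---|---|---|---|
| Top 20% | >99.9% (0.560) | >99.9% (0.420) | >99.9% (0.280) | >99.9% (0.140) |
| Top 50% | >99.9% (0.319) | >99.9% (0.239) | 99.9% (0.160) | 95% (0.080) |
| Top 70% | 99.7% (0.199) | 98% (0.149) | 90% (0.099) | 61% (0.050) |
| Top 80% | 90% (0.140) | 80% (0.105) | 62% (0.070) | 35% (0.035) |
| Top 90% | 44% (0.078) | 34% (0.058) | 24% (0.039) | 14% (0.019) |
| No selection | 5% (0) | 5% (0) | 5% (0) | 5% (0) |

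Simulation agreed with the formula: 99.9% at q = 0.5, rho = 0.8; 34% at q = 0.8, rho = 0.9; 15% at q = 0.9, rho = 0.9.

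**The 6-month to last-visit change.** Under the same model its expected value with no drug effect is (rho at 6 months − rho at last visit)·λ. This is zero only if baseline correlates equally with both visits. With assumed correlations of 0.8 and 0.6 and above-median selection it is (0.8 − 0.6) × 0.798 = 0.16 SD, the same as the baseline-to-6-month artefact at rho = 0.8.

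**The case against.** The protocol is open about being a retrospective analysis of treated patients, and Section 7 in effect defines efficacy as score change, so part of the issue is terminology. That is fair, but the word still carries a causal claim, and Section 8.8 does not warn the reader.

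Three stronger readings are tempting, and the documents support none of them.

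- *Significance is assured even if the drug does nothing.* This needs strong selection on the baseline score. The inclusion criteria require a confirmed diagnosis of moderate-to-severe disease, but they give no BSA, PASI or DLQI cut-off and do not tie the diagnosis to the baseline visit. Where most source patients already pass the cut, the chance falls well below certainty.
- *The plan will read a paired p-value as proof of efficacy.* No paired test, significance level or decision rule appears in the plan. The calculation shows what such a test would be worth if it were run.
- *An observed improvement would be only artefact.* Small shifts reach significance at n = 400 because n is large. A large observed change could not be put down to a regression artefact of modest size, although retention selection and other treatment would still be unquantified. The documents give no expected change for comparison.

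**Conclusion.** The point stands on design grounds. With no untreated or alternative-treatment group, and entry conditioned on at least 1 year of treatment, the planned before-after change cannot deliver an efficacy conclusion. This rests on the text alone.

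The regression-to-the-mean figures are illustrative. At about 400 patients that mechanism alone could produce a significant change, with a chance anywhere from 5% to over 99% depending on inputs the documents do not give. Its size is about 0.04 to 0.32 SD of the source-population score when the top 50% to 80% are selected and the correlation is 0.6 to 0.9; it is larger under harsher selection. The magnitude of the change is therefore more informative than its p-value. The direction of the retention bias is plausible, but its size is unknown.

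**What to change.** - **Sections 6, 7 and 8.1:** restate the aim and primary objective as describing the change in BSA, PASI and DLQI from baseline to 6 months and to last visit in patients treated with Enbrel for at least 1 year.
- **Section 8.6:** name the mean within-patient change, with its 95% confidence interval, as the primary analysis for each score and time. State that a p-value on that change will not be taken as evidence of efficacy.
- **Section 8.8:** state that the lack of a control, the 1-year retention selection and possible regression to the mean limit the conclusion.
- **Optional:** report the 6-month to last-visit change as a descriptive contrast. Say that it is less affected by starting-score selection but not free of it, and that it is still conditional on retention.

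The cost is wording in five sections and a short analysis specification, with no new data collection. The downside is a weaker headline claim.

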8.2.1. Inclusion Criteria

Patients must meet each of the following inclusion criteria to be eligible for inclusion in the study:

1. Confirmed diagnosis of moderate-to-severe plaque psoriasis and receiving etanercept treatment for a minimum duration of 1 year.
2. Age ≥ 18 years old.
3. No history of using a biological treatment, other than etanercept, for treatment of moderate to severe plaque psoriasis or any other reason.

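### The last-visit comparisons have no defined time since first dose: they show only change to last recorded visit, and the unadjusted adherence-group contrast there can be biased

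*Combined protocol and SAP*

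**What the plan says.** Section 7 gives the primary objective two comparisons with baseline: one at 6 months after starting treatment, and one described as "compared to the last visit follow-up BSA, PASI, and DLQI scores". Section 8.1 collects the three scores at the same points and then compares the adherence groups at baseline, "6-months after Enbrel treatment, and at last visit follow-up after Enbrel treatment". No section gives the last visit a time since first dose, a window, a cut-off rule, or a statement of whether the patient must still be on treatment.

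The only bounds are indirect:

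- Section 8.2.1 requires patients to be "receiving etanercept treatment for a minimum duration of 1 year".
- Section 6 describes use in Iraq as "starting in 2014 when the first psoriasis patients received the first dose of Enbrel".
- Section 5 puts the end of data collection at "01 October 2020". The column is headed as planned dates, but the amendment log in section 4 records "Aligned dates with Study Report".
- Section 8.1 describes the adherent group as "adherent to Enbrel treatment for one and seven years".

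Section 8.6 describes covariates and sets out unadjusted group comparisons (chi-squared, t-test, Kruskal-Wallis). It has no within-patient analysis, no summary of follow-up time, and no stratification or adjustment by follow-up time or baseline score. Section 8.8 names missing data as the only limitation.

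**The concern.** A score taken at whatever visit happens to be last is measured at a different time in each patient. A single summary of it mixes durations, and what it says depends on how long patients happened to be followed as well as on response. Half of the primary objective rests on this quantity.

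The same visit is used to contrast adherent with non-adherent patients. If one group was followed for longer and scores drift with time, or if the groups started from different scores, the unadjusted difference carries that imbalance along with any association with adherence. As planned, the report would contain nothing from which a reader could judge how unequal the follow-up was.

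**Working it through.** The plan states no figure to reproduce. The check is date arithmetic, then the structure of the comparison.

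**Inputs.** First doses in 2014, exact date not given, so 1 January and 31 December are both used (section 6). End of data collection 1 October 2020 (section 5). Minimum treatment 1 year (section 8.2.1). About 400 patients (section 8.4).

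**1. Longest possible time from first dose to last visit.** 1 January 2014 to 1 October 2020 is 6.75 years; 31 December 2014 to 1 October 2020 is 5.75 years. Reaching this ceiling requires that patients who started in 2014 are in this registry and were seen close to the cut-off.

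**2. Shortest.** About 1 year, from the treatment minimum. This bounds treatment duration, not the assessment: nothing prevents the last *recorded score* from being earlier than 1 year.

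**3. Consistency of the ceiling.** Seven years before 1 October 2020 is 1 October 2013, before the stated first use. The shortfall is 7 − 6.75 = 0.25 to 7 − 5.75 = 1.25 years. The seven-year figure in section 8.1 therefore cannot hold with the dates in sections 5 and 6, and the ceiling in step 1 would move if any of these were corrected.

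**4. Who could have five years of follow-up.** Only patients with a first dose by 1 October 2015. The documents give no accrual pattern and no last-visit dates, so the share could be anything from none to all.

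**5. How a last-visit mean depends on the follow-up mix (assumed values throughout).** Take mean PASI improvement at 1, 3, 5 and 7 years, with the 7-year point standing in for the longest follow-up. Let the waning course be 75, 65, 55, 45% and the rising course 65, 70, 75, 80%.

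| Mix over the four times | Mean years | Waning | Rising |
|---|---|---|---|
| 0.55, 0.25, 0.15, 0.05 | 2.4 | 68.0% | 68.5% |
| 0.25, 0.25, 0.25, 0.25 | 4.0 | 60.0% | 72.5% |
| 0.05, 0.15, 0.25, 0.55 | 5.6 | 52.0% | 76.5% |

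For example, 0.55×75 + 0.25×65 + 0.15×55 + 0.05×45 = 68.0. With mostly short follow-up, opposite long-term courses give almost the same figure; with the waning course alone, the figure moves from 68.0% to 52.0% as the mix changes. None of these values is an estimate for this study.

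**6. The group comparison.** Suppose the expected last-visit score is a + γ·group + β·baseline + s·time. The unadjusted group difference is then γ + β·(difference in mean baseline) + s·(difference in mean time). The last two terms vanish only if the groups are balanced or the coefficients are zero. The documents give none of these quantities, so neither the size nor the sign of the bias can be computed.

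**The case against.** Last recorded visit is an ordinary endpoint in retrospective registry work and a legitimate description of status. Sections 7 and 8.1 never call it a long-term or durable effect. That stands, and the point is limited to definition, labelling and reporting for the primary comparison.

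A reader might infer that the plan promises five-year efficacy, because section 6 speaks of local data on patients "in patients with moderate-to-severe plaque psoriasis after five years of use". The documents do not support that reading. The phrase is background, may refer to national experience, and is not a time point for any objective.

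A reader might also infer that most patients cannot have five years of follow-up. With even accrual to 1 October 2019 and every last visit at the cut-off, the five-year share would be 0.75/4.75 = 16% to 1.75/5.75 = 30%. Both conditions are assumptions without support in the documents, so this is not a finding.

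That a pooled mean will be reported is likewise inferred: section 8.6 specifies no mean change. It does, however, plan no split by duration.

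Finally, the group comparison lies outside the primary objective, and section 8.1 compares the groups at baseline, so an imbalance would be visible. Visible is not the same as allowed for, and follow-up time would remain unreported.

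**Conclusion.** The point holds in limited form. The last visit is undefined in time, and the documents' dates allow a spread from about 1 year to 5.75-6.75 years, subject to the date conflict with section 8.1. The last-visit result is sound as change to last recorded visit and not as an effect at a stated long-term time. The adherence-group difference at that visit is open to bias from unequal follow-up or baseline imbalance. It would be too strong to say that it *is* biased: that would require the groups to differ in baseline score, or to differ in follow-up with scores that change over time, and the documents show neither.

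The 6-month comparison is nominally timed, so it does not share this spread, but it too has no visit window.

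**What to change.** In section 8.6:

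1. Define the last visit as the latest recorded score up to the data cut-off, flagged as on or off treatment. Report time from first dose to that visit (median, quartiles, range) overall and by adherence group.
2. Label the result *change to last recorded visit* and do not present it as an effect at a stated long-term time. Any table by year since first dose should be descriptive only, with counts: the bands contain different patients, and an early band can mix recent starters with patients who stopped attending, so they are not a time course.
3. Keep the unadjusted group test and report beside it a regression of last-visit score on group and baseline score. Add time since first dose only as a sensitivity analysis, because it is post-baseline and may depend on adherence or response.

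In section 8.8, add unequal follow-up as a limitation. Separately, reconcile the one-and-seven-year wording in section 8.1 with the dates in sections 5 and 6 and the first-year adherence objective in section 7; the regression's group term depends on that definition.

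**Cost.** No new patients are needed. First-dose and last-visit dates must be available; section 8.3 lists no variables, so a re-extraction may be required. Since collection has ended, these analyses must be labelled as added after data collection.

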8. RESEARCH METHODS

8.1. Study Design

This is a retrospective analysis of approximately 400 Iraqi patients diagnosed with moderate-to-severe plaque psoriasis that received Enbrel as treatment for disease.

Baseline, 6 months after initiation of Enbrel treatment and last visit follow-up, BSA, PASI, and DLQI scores for identified patients will be collected and used to evaluate efficacy. Patients will be further divided into 2 groups according to their adherence to Enbrel treatment (The adherent group will include the patients who were adherent to Enbrel treatment for one and seven years, and the non-adherent group will include patients who did not adhere to Enbrel). There will then be a comparison between both groups; in BSA, PASI, and DLQI scores at baseline, 6-months after Enbrel treatment, and at last visit follow-up after Enbrel treatment.

Patient demographic information (eg, age gender, disease duration) will be analyzed throughout the study.

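### Section 8.1 defines adherence by a seven-year period that no patient can reach; the likelier range reading gives each patient a different assessment window and confounds the group comparison

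*Combined protocol and SAP*

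**What the plan says.** Section 8.1 divides patients into two groups by adherence and compares BSA, PASI and DLQI between them at baseline, at 6 months and at last visit. The first group is to hold those who were "adherent to Enbrel treatment for one and seven years". For the second the rule is: "the non-adherent group will include patients who did not adhere to Enbrel". The protocol gives no adherence measure, cut-off or assessment window beyond this.

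Four other places bear on the rule:

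- Section 6 describes national use as "starting in 2014 when the first psoriasis patients received the first dose of Enbrel".
- Section 5 sets the end of data collection at "01 October 2020".
- Section 7 states the secondary objective as "Determine the first year adherence of patients with moderate-to-severe plaque psoriasis on a Enbrel treatment".
- Sections 8.2, 8.2.1 and 8.2.2 admit only patients with at least one year of etanercept treatment and exclude those with less.

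Section 8.6 plans unadjusted between-group tests and no adjusted analysis.

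**The concern.** The sentence in Section 8.1 is the only text that assigns patients to the two groups, and every adherent versus non-adherent comparison rests on it. Its seven-year part does not fit the study's own dates. The obvious repair, reading it as a range from one to seven years, creates a different problem. Adherence would be judged over whatever follow-up each patient happens to have, so a patient who started early has more time in which to be labelled non-adherent than one who started late.

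Group membership would then partly reflect start year and length of follow-up. The last-visit scores are also taken at a time that varies between patients, so that comparison is the most exposed. Nothing in Section 8.6 would separate adherence from follow-up time.

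Because the registry data already exist, an open rule also allows the grouping to be settled after the scores have been seen.

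**Working it through.** **Step 1: longest possible follow-up.** The inputs are a first dose in 2014 (Section 6, no day or month given) and the end of data collection on 1 October 2020 (Section 5). Follow-up in years is days divided by 365.25.

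| Assumed first dose | Years to 1 October 2020 |
|---|---|
| 1 January 2014 | 2465 / 365.25 = 6.75 |
| 1 July 2014 | 6.25 |
| 31 December 2014 | 5.75 |

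No start date in 2014 reaches 7.0 years. Counting instead to the planned report date, 1 September 2021, gives 6.67 to 7.67 years, but that is eleven months after data collection closed. The plan's figure of seven years therefore cannot be reproduced. Section 6 itself speaks only of this: "Iraq has over 5 years of experience in using Enbrel as a treatment for psoriasis patients".

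**Step 2: the range reading.** If the phrase means one to seven years, a ceiling of seven excludes nobody, since the maximum is 6.75. The assessment window then runs from 1 year to at most 6.75 years, depending on the patient's start date and last visit.

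**Step 3: how the label depends on follow-up.** The protocol gives no stopping rate, so the following is illustrative. Assume that:

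- non-adherence means stopping treatment at any time during follow-up;
- patients who stopped after completing one year are eligible;
- the yearly stopping rate r is constant after year 1.

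Nobody in the study can have stopped in year 1, because of the entry rule. With T years of follow-up, the chance of the non-adherent label is 1 − (1 − r)^(T − 1).

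| Follow-up T | r = 5% | r = 10% | r = 20% |
|---|---|---|---|
| 1 year | 0% | 0% | 0% |
| 3 years | 1 − 0.95^2 = 10% | 1 − 0.90^2 = 19% | 1 − 0.80^2 = 36% |
| 6.75 years | 1 − 0.95^5.75 = 26% | 1 − 0.90^5.75 = 45% | 1 − 0.80^5.75 = 72% |

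Within each column the underlying behaviour is identical; only the follow-up differs. The protocol gives no distribution of follow-up, so the first and last rows are the extremes and not a typical contrast.

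**Step 4: comparison with the secondary objective.** Section 7 asks for adherence in the first year. The one-year part of the Section 8.1 phrase fits that; the seven-year part, or a one-to-seven-year range, is a different quantity.

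**Step 5: comparison with eligibility.** Simply moving to a first-year window is not enough. If adherence means remaining on treatment, Sections 8.2 to 8.2.2 have already removed everyone who stopped in year 1. First-year adherence would then be close to 100% by construction, and the non-adherent group close to empty.

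**The case against.** The best defence is that a word was dropped and a range was meant. The text has other slips of language, one year matches the eligibility floor, and 2014 to 2020 spans seven calendar years. This is plausible, and it disposes of a stronger inference: that the adherent group is empty and none of the roughly 400 patients can qualify. That follows only if adherence at both one and seven years is required of each patient. The phrase can also be read as a range, or as patients adherent for one year together with those adherent for seven. The documents do not make the strictest reading the plan. The range reading does not rescue the rule, however, for the reasons in steps 2 and 3.

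Three further points against the concern stand in part:

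- *The rule does not wholly conflict with Section 7.* Its one-year part fits the secondary objective. Section 7 also does not say that the group comparison must use the first-year window.
- *The dependence on follow-up needs a particular meaning of non-adherence.* If any lapse or stop counts, the label becomes more likely with time. A proportion-of-doses measure would not rise mechanically in this way. The protocol says neither.
- *The entry rule lowers the figures.* A reader might apply yearly rates from the first dose and obtain 5%, 10% or 20% at 1 year and 29%, 51% or 78% at 6.75 years (1 − 0.95^6.75 and so on). For stopping, that ignores the one-year entry rule; the table in step 3 applies it.

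**Conclusion.** The concern holds in a limited form. The seven-year part of the rule cannot be met: the maximum follow-up is 6.75 years, taking the 2014 first dose from Section 6 and no follow-up beyond 1 October 2020. On the likelier range reading, the window differs between patients. If any lapse or stop counts as non-adherence, the unadjusted comparisons are confounded with follow-up time and start year, most of all at last visit. The illustrative size is about 0% labelled non-adherent at 1 year against 26%, 45% or 72% at 6.75 years, for assumed yearly stopping rates of 5%, 10% or 20%. The direction of any resulting bias in the scores cannot be determined from the documents.

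A reader might infer that the main efficacy result is compromised. It is not: the primary objective in Section 7 compares baseline with 6-month and last-visit scores and uses no adherence groups. The problem is confined to the group comparison in Section 8.1 and the first-year adherence estimate.

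**What to change.** In Section 8.1, delete the one-and-seven-years wording and classify every patient over one common window: the first 365 days from the first Enbrel dose, which matches the secondary objective. Fix one numeric cut-off before analysis, based on doses or dispensing recorded in the registry and not on persistence.

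If the registry holds only start and stop dates, reconcile Sections 7, 8.1 and 8.2. Either drop the adherent versus non-adherent comparison, or state that first-year adherence cannot be estimated in a population selected for completing one year.

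Describe discontinuation after year 1 separately, with a Kaplan-Meier curve conditional on completing one year and censored at last visit or 1 October 2020. If the comparison has already been run, the report should state the rule actually used and add results under the common window.

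The cost is a short rewrite and a little more analysis. The cut-off depends on dosing or dispensing data, which Section 8.3 does not confirm the registry holds; the Kaplan-Meier curve needs only treatment and visit dates. One weakness remains: a 365-day window partly post-dates the 6-month scores, so the 6-month group comparison should be labelled descriptive.
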